## Glossary of terms

Assessment	A procedure used to generate data required by the study
Enrollment	Point/time of patient entry into the study; the point at which informed consent must be obtained (i.e. prior to starting any of the procedures described in the protocol)
Epoch	The planned stage of the subjects' participation in the study. Each epoch serves a purpose in the study as a whole. Typical epochs are: determination of subject eligibility, wash-out of previous treatments, exposure of subject to treatment or to follow-up on subjects after treatment has ended.
Investigational drug	The drug whose properties are being tested in the study; this definition is consistent with US CFR 21 Section 312.3 and is synonymous with "investigational new drug" or "investigational medicinal product."
Investigational treatment	All investigational drug(s) whose properties are being tested in the study as well as their associated treatment controls. This includes any placebos, any active controls, as well as approved drugs used outside of their indication/approved dosage or tested in a fixed combination. Investigational treatment generally does not include other treatments administered as concomitant background therapy required or allowed by the protocol when used within approved indication/dosage
Subject Number	A number assigned to each patient who enrolls into the study
Part	A subdivision of a single protocol into major design components. These parts often are independent of each other and have different populations or objectives. For example, a single dose design, a multiple dose design that are combined into one protocol, or the same design with different patient populations in each part.
Period	A subdivision of a cross-over study
Premature patient withdrawal	Point/time when the patient exits from the study prior to the planned completion of all investigational/study treatment administration and all assessments (including follow-up)
Stop study participation	Point/time at which the patient came in for a final evaluation visit or when study/investigational treatment was discontinued whichever is later
Study drug/ treatment	Any single drug or combination of drugs administered to the patient as part of the required study procedures; includes investigational drug (s), active drug run-ins or background therapy
Study/investigational treatment discontinuation	Point/time when patient permanently stops taking study/investigational treatment for any reason; may or may not also be the point/time of premature patient withdrawal
Variable	Information used in the data analysis; derived directly or indirectly from data collected using specified assessments at specified time points

## Protocol synopsis

Protocol number	CFTY720DTR05
Title	Effect of Fingolimod on neurodegeneration, brain atrophy and cognitive impairment in relapsing remitting multiple sclerosis patients
Brief title	Effect of Fingolimod on neurodegeneration, brain atrophy and cognitive impairment in relapsing remitting multiple sclerosis patients
Sponsor and Clinical Phase	Novartis Phase IV
Investigation type	Drug
Study type	Interventional
Purpose and rationale	
Multiple sclerosis (MS) is a neurodegenerative disease in which both demyelination and axonal loss occur.
 
Cognitive impairment is a major problem in MS and adversely affects patients' quality of life. Cognitive decline may appear early in the disease process and has been reported even at disease onset. It has previously been shown that a cognitive impairment is present in 53.7% of RRMS patients evaluated at the early disease stage during the onset of neurological symptomatology. (7,8)
 
Our aim in this study is to investigate the effect of fingolimod on cognitive performance.
 
Neuronal loss has been historically detected through MRI quantification of brain volume. Gray matter atrophy occurs in patients with relapsing forms of MS early in the disease course, has a major relationship to physical disability and cognitive impairment, and is a putative measure of neuroprotective therapeutic effects. (9)
 
The paired thalamic nuclei are gray matter structures on both sides of the third ventricle and are involved in a wide range of neurological functions including motor, sensory, integrative, and higher cortical functions.(10) Thalamic location, unique neurologic functions, widespread cortical and subcortical connections and vulnerability to MS pathology from the earliest clinical disease stages make it a critical structure for examining neurodegeneration in MS (11,12)
 
Our other aim in this study is to investigate the effect of fingolimod on brain gray matter atrophy and thalamic atrophy.
 
Cognitive dysfunctions are mainly associated with brain atrophy especially cortical grey matter. (13,14) In this study we will investigate the correlations between the effects of fingolimod on cognitive performances and MRI data.
 
For diagnostic, prognostic and treatment monitoring purposes, biomarkers which reflect the various neurodegenerative processes, would be helpful. The biomarker has to be central nervous system (CNS) specific, and available in concentrations that could be measured in cerebrospinal fluid (CSF) or blood. Serum and CSF oxysterols and cholesterol precursors have been linked to pathological processes in MS in previous studies, and seem to be promising candidate biomarkers. (15-17)

	
In this study we will evaluate the effect of fingolimod treatment on the serum levels of a brain specific cholesterol metabolite 24S-hydroxycholesterol (24OHC) which is a biomarker reflecting neurodegeneration. (22)
 
We will also evaluate the effect of fingolimod on plasma levels of osteopontin which is a pro-inflammatory cytokine and matrix metalloproteinase which have a role in the pathology of multiple sclerosis.(23,24)

Primary Objective(s) and Key Secondary Objective	
Primary objective of this study is:
 
-To investigate the effects of Fingolimod on cognitive performance in highly active relapsing remitting multiple sclerosis patients

Secondary Objectives	
Secondary objectives of this study are:
 
-To investigate the correlation between the effect of fingolimod on cognitive performances and MRI data.
 
-To evaluate the effect of fingolimod on biomarkers (24 hydroxy cholesterol, osteopontin and matrix metalloproteinases) related to neurodegeneration
 
-To investigate the effect of fingolimod on brain gray matter atrophy and thalamic atrophy.

Study design	
This is a 24-month, open-label, multicenter study with a single treatment arm design.

Population	
We will recruit a minimum of 80 relapsing remitting MS (RRMS) patients according to the McDonald criteria. All subjects will sign an informed consent that will be approved by the Ethics Committee.

Inclusion criteria	
 
1. Diagnosed with RRMS as described in 2010 McDonald criteria
 
2. Provided written informed consent prior to any intervention
 
3. Female or male patients aged 18-65 years
 
4. Unresponsive to treatment with a beta interferon or glatiramer acetate for a minimum of one year at and at adequate dose and with high disease activity
 
 
(Unresponsive patients: patients with no changes in relapses, increased relapses, severer relapses with one-year treatment or those who had had at least one relapse during the past one year under previous treatments and one or multiple contrast enhancing lesions in cranial MRI or increased T2 lesions in successive MRIs)
 
 
5. EDSS score below 5.5 at screening
 

Exclusion criteria	
 
1. Patients with primary or secondary progressive or progressive relapsing MS
 
2. Patients with known contraindications for fingolimod treatment.
 
3. Other coexistent autoimmune diseases including Hashimoto thyroiditis, systemic lupus erythematosus, rheumatoid anthritis, psoriasis etc.
 
4. Patients with any of the following cardiovascular conditions: 
 
• Resting heart rate < 45 bpm/min
 
 
 

	
 
• Cardiac failure at any time during the first study visit (Class III as per NYHA classification) or significant heart disease as judged by the physician
 
• Myocardial infarction during the last 6 months
 
• History of Mobitz Type II grade 2 AV block
 
• Past or current grade 3 AV block
 
• Confirmed history of sick sinus syndrome or sino-atrial heart block
 
• arrhythmia requiring current treatment with Class Ia drugs (ajmaline, disopyramid, procainamide, quinidine)
 
• hypertension uncontrolled with medication
 
 
 
5. History of malignancy of any organ system (other than localized basal cell carcinoma of the skin), treated or untreated, within the past 5 years, regardless of whether there is evidence of local recurrence or metastases.
 
6. Pregnant or nursing (lactating) women, where pregnancy is defined as the state of a female after conception and until the termination of gestation, confirmed by a positive hCG laboratory test.
 
7. Negative for varicella-zoster virus IgG antibodies at screening. Patients who have negative results for varicella-zoster virus IgG antibodies can be included in the study after vaccination for varicella-zoster virus.
 
8. Active systemic bacterial, viral or fungal infections, or diagnosis of AIDS, Hepatitis B, HepatitisC infection defined as a positive HIV antibody, Hepatitis B surface antigen or Hepatitis C antibody tests, respectively
 
9. History of previous fingolimod therapy
 
10. Patient who received any of the treatments below:             
 
a. Corticosteroids or adrenocorticotrophic hormone (ACTH) during the last 1 month
 
b. Immunosuppressive medications such as azathioprine or methotrexate etc.
 
c. Immunoglobulin treatment during the last 3 months
 
d. Cladribine, cyclophosphamide, mitoxantrone, natalizumab at any time
 
 
 

Investigational and reference therapy	Fingolimod
Efficacy assessments	Cognitive tests, MRI ,biomarkers, EDSS
Safety assessments	This study does not include any planned safety analysis
Other	Not Applicable

assessments	
Data analysis	Data analysis will be performed after all of the data is collected from the enrolled patients. All RRMS patients will be accepted as the analysis sets.
Key words	Fingolimod, neurodegeneration, brain, atrophy, cognitive, impairment, relapsing, remitting, multiple, sclerosis

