### **3.3 Rationale for choice of comparator**

A comparator arm is not applicable for this study

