## 6.4 Efficacy

### 6.4.1 Cognitive Tests

The Brief International Cognitive Assessment for Multiple Sclerosis (BICAMS) Battery test is the primary efficacy assessment criteria. Cognitive tests will be performed to RRMS patients at baseline and at months 6, 12 and 24 at the study center.

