validated with brain MR total lesion area and right superior frontal atrophy, 44 MR T1 and FLAIR lesion volume, BPF and third ventricular width and MR diffusion measures.

Football	Paper	Folder	Candy
Notebook	River	Boxing	Envelope
Island	Tennis	Mountain	Valley
Billiards	Cake	Pie	Ice cream

**Brief Visuospatial Memory Test (BVMTR)** will assess visual/spatial memory in BICAMS. In this test, six abstract designs such as the figure shown below are presented for 10 seconds. The display is removed from view and patients render the stimuli via pencil on paper manual responses. Each design receives from 0 to 2 points representing accuracy and location. Thus, scores range from 0 to 12. There will be three learning trials, and the primary outcome measure is the total number of points earned over the three learning trials. Because there is little evidence that the delayed recall trial adds to discriminant validity in MS, as in the MATRICS consensus battery, only the initial learning trials will be included for BICAMS.

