### **6.4.4 Expanded Disability Status Scale (EDSS)**

EDSS is a scale for assessing neurologic impairment in MS (Kurtzke 1983) including (1) a series of scores in each of eight functional systems, and (2) the EDSS steps (ranging from 0 (normal) to 10 (death due to MS)). The functional systems are Visual, Brain Stem, Pyramidal, Cerebellar, Sensory, Bowel & Bladder, Cerebral and Other functions. It is recommended that fatigue is not included in the Cerebral score of the EDSS.

EDSS will be assessed by the investigator at each site, who has successfully completed his/her certification requirements. EDSS assessments are scheduled at screening and at month 3, 6, 12, 18 and 24.

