#### **9.4.3.2 Statistical Methods by Evaluation of Study Objective**

##### **Primary Objective:**

Primary objective of the study will be evaluated by the statistical methods which are stated below:

- Calculated scores of BICAMS (SDMT, CVLT2 and BVMTR) at baseline, 12th month and 24th month will be compared by using Repeated Measures ANOVA (if variables are non-normally distributed Friedman Test).

Post-Hoc comparisons will be done with Tukey test. (if Friedman test was used, Wilcoxon Signed Rank test will be used for Post-Hoc comparisons.)

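### BVMTR, one of the three primary scores, is graded from drawings with nothing masking the visit from the scorer, so an upward scoring drift on treatment could not be told apart from cognitive improvement

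*Combined protocol and SAP*

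**What the plan says.** The synopsis gives the design, and section 3.1 repeats it: "This is a 24-month, open-label, multicenter study with a single treatment arm design". Section 3.3 adds: "A comparator arm is not applicable for this study". Any effect of treatment therefore has to be read from change over time within patients.

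Section 6.4.1 makes BICAMS the primary efficacy assessment. Section 9.4.3.2 lists what is tested for the primary objective: "Calculated scores of BICAMS (SDMT, CVLT2 and BVMTR) at baseline", month 12 and month 24, by repeated measures ANOVA or, if the data are not normal, Friedman's test. No one of the three scores is named as decisive.

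On BVMTR, section 6.4.1 says that "patients render the stimuli via pencil on paper manual responses" and that "Each design receives from 0 to 2 points representing accuracy and location". With six designs this gives 0-12 per trial, and "the primary outcome measure is the total number of points earned over the three learning trials".

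On who does this, the section says only: "Cognitive tests will be performed to RRMS patients at baseline and at months 6, 12 and 24 at the study center". It does not say who scores the drawings, by what criteria, whether the scorer knows the visit, or whether there is second or central scoring. The plan does set a rater rule for EDSS in section 6.4.4: "EDSS will be assessed by the investigator at each site, who has successfully completed his/her certification requirements". It sends MRI scans to one center (sections 6.4.2 and 9.4.2). There is no adjudication committee (section 8.5).

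**The concern.** In a randomized trial the scorer's knowledge of the arm is the threat. Here every patient receives fingolimod after baseline, so knowing the visit is the same as knowing whether the patient has been treated. Section 9.4.3 states the expected direction, which is improvement on the cognitive tests.

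BVMTR leaves more room for this than a count of spoken answers does, because each drawing gets a graded mark for accuracy and location. If marks at months 12 and 24 were on average a little higher than the same drawings would have earned at baseline, the difference would go straight into the change score. Without a control group there is nothing against which to detect or subtract it. A larger sample does not help: the bias stays the same while the standard error shrinks.

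At stake is whether a BVMTR gain can be reported under the primary objective as a change in the patients and not a change in the marking. The drawings are permanent paper records, so this part of the assessment can be masked even though treatment is open.

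**Working it through.** **Inputs from the plan**
- BVMTR (section 6.4.1): 6 designs, 0-2 points each, 3 trials. Drawings per visit = 6 x 3 = 18; maximum total = 6 x 2 x 3 = 36.
- Two-sided 5% level (section 9.4.3.1).
- 80 enrolled, 10% expected loss (section 9.6): 80 x 0.90 = 72 completers.

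**The plan's own figure.** Section 9.6 gives a minimum of 73 and names no formula. A precision formula for a 5% proportion with a margin of 5 percentage points reproduces it: 1.96² x 0.05 x 0.95 / 0.05² = 72.99, so 73. The figure rests on SDMT; the plan gives no target, SD or sample-size argument for BVMTR.

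**Inputs assumed, not in the documents**
- SD of the BVMTR change from baseline to month 24: 4 to 8 points.
- Average net scoring drift: 0.5 or 1 point on the total.
- No true change.

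**Method.** A paired t-test of month 24 against baseline stands in for the planned three-visit analysis. With drift b and SD of change s, SE = s/√72 and the noncentrality is b/SE, on 71 degrees of freedom. The critical value is 1.994. The probability of a significant result comes from the noncentral t distribution, both tails.

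| SD of change | SE | b/SE at 0.5 | P(significant), 0.5 point | b/SE at 1 | P(significant), 1 point |
|---|---|---|---|---|---|
| 4 | 0.471 | 1.061 | 0.182 | 2.121 | 0.553 |
| 5 | 0.589 | 0.849 | 0.133 | 1.697 | 0.388 |
| 6 | 0.707 | 0.707 | 0.107 | 1.414 | 0.286 |
| 8 | 0.943 | 0.530 | 0.082 | 1.061 | 0.182 |

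Without drift the figure is 0.05, of which 0.025 is in the direction of improvement. With drift nearly all of the probability lies in that direction.

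**Drift that gives an even chance of a false finding.** This is about 1.994 x SE: 0.94 point at SD 4 and 1.88 points at SD 8. Divided by 18 drawings, it is 0.05 to 0.10 point per drawing.

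**Effect of more patients.** At SD 4 and a 1-point drift, the probability rises from 0.553 with 72 patients to 0.598 with 80.

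**The case against.** The strongest reply is that the bias is supposed, not shown. That the marking leaves room for leniency is inferred from a 0-2 grade for accuracy and location. The plan reproduces no scoring criteria and names no scorer, so the actual room is unknown. Both the drift and the SD are assumed. One point on one of 18 drawings sounds trivial, but it would have to be the net average over all patients and several sites, always in the same direction. This stands, and it limits the figures to an illustration.

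Second, the only numerical target and the sample-size argument concern SDMT (sections 9.4.1 and 9.6). That also stands. It does not remove BVMTR from the primary analysis, because section 9.4.3.2 tests all three scores and ranks none.

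Third, larger threats survive masked scoring. The same battery is given four times, without a comparator, to patients selected for high disease activity, and the tester giving it knows the visit. This is correct, and masked scoring would not make a BVMTR gain attributable to fingolimod. It removes one source of bias, which is worth doing at this price.

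A reader might infer that the open-label single-arm design is itself the error. It is a declared choice, and the point here asks only for masked scoring.

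A reader might also extend the point to MRI and serum samples. The documents do not support that: volumes come from SIENAX, FIRST and FreeSurfer, with automatic thalamic segmentation (section 9.4.2), and laboratory samples are processed centrally (section 8.3). No comparable graded judgement is described for either.

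**Conclusion.** The point holds as a preventable weakness in one of three primary scores. The plan has a graded score, a purely before-after contrast, a stated expected direction and no masking of the visit. Scoring drift and treatment effect therefore cannot be separated in the planned analysis.

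Its size cannot be read from the documents. Over the assumed SD range with 72 completers, a half-point average drift raises the chance of a false significant result from 5% to about 8-18%, and a one-point drift raises it to about 18-55%. These figures depend on the assumed SD, on the assumed drift being a net average in one direction, and on the paired t-test as a stand-in.

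The plan does not support saying that BVMTR scores will be biased, or that the trial's conclusion turns on BVMTR.

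**What to change.** In section 6.4.1, add that all BVMTR response sheets are kept. After each patient's last visit, existing site staff other than the scorer cover the date and visit and shuffle that patient's sheets. One trained site scorer, where possible not the person who gave the tests, then scores all of them in that order. In section 9.4.3.2, state that these masked scores are the BVMTR scores analyzed. Scoring all of a patient's sheets together also means that any constant leniency of the scorer cancels in the change from baseline.

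Cost and limits:
- A protocol wording change and a small covering and coding task at sites; no new visit, test or outside reader.
- BVMTR scores are not available until the patient's last visit. The main analysis is unaffected, since section 9.1 places it after all data are collected. Any yearly interim analysis (sections 3.4 and 9.7) would lack BVMTR for patients still in follow-up, and the plan should say so.
- Masking is incomplete where the scorer also gave the tests and may recognize the drawings.
- Practice effects, regression to the mean and unmasked test administration are not addressed and should be named as limits when results are reported.

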## 1 Introduction

### 1.1 Background

Multiple sclerosis (MS) is the leading cause of neurological disability in young adults and the most common demyelinating disorder of the central nervous system. It is widely regarded as a chronic autoimmune disorder encompassing both inflammatory (myelin destruction) and degenerative (axonal loss) features. Disease onset is thought to be mediated by T lymphocytes that recognize myelin antigens, cross the blood brain barrier and drive the immune response against oligodendrocytes and myelin sheaths. MS typically presents in relapsing forms, either with a relapsing-remitting (RRMS) or secondary progressive (SPMS) course. Patients suffer acute self-limiting attacks (relapses) of neurological dysfunction followed by complete or incomplete remission. Between relapses, patients are either neurologically and symptomatically stable (RRMS) or continue to deteriorate in function unrelated to relapses (SPMS). Currently available therapies for patients with RRMS (interferon  $\beta$  and glatiramer acetate) have partial efficacy (about 30-40% reduction in relapse rate and at best a modest effect on disability progression). These agents are biologic parenteral treatments requiring injections associated with side effects (injection site reactions, flu-like symptoms). Therefore, there is a strong medical need for a safe and effective oral treatment of MS. (1)

Fingolimod is a novel, orally active, synthetic small molecule in clinical development for MS. Fingolimod is rapidly phosphorylated *in vivo*, and fingolimod-phosphate (fingolimod-P) acts as agonist of G protein-coupled receptors for sphingosine-1 phosphate (S1P). More particularly, fingolimod-P acts as 'super agonist' of the S1P1 receptor on thymocytes and lymphocytes, inducing internalization of that receptor. This renders these cells unresponsive to S1P1 signaling, thus depriving them of a signal necessary for egress from lymph nodes and secondary lymphoid tissues. The downstream result of this fingolimod induced interdiction of S1P1 signaling is a marked reduction in the number of both B and T lymphocytes in the intravascular compartment and a decrease in recirculation of these cells to extravascular compartments, including the CNS. In animal immunization models, fingolimod neither impaired T-cell activation, expansion, and memory, nor antibody production by B-cells. However, fingolimod will reduce the ability of an expanded number of activated effector lymphocytes to return to a site of inflammation or infection.

Emerging preclinical data suggest that the mechanism of action of fingolimod may involve CNS effects in addition to the effect on reducing lymphocyte infiltration into the CNS. Fingolimod penetrates into the brain, accumulating predominantly in the white matter. S1P receptors are widely expressed in the CNS, in particular on neurons and glial cells and there is evidence for S1P signaling on CNS cells with involvement in e.g. survival and modulation of process formation in both neurons and oligodendrocytes, neurogenesis, and neuroexcitability.(2) *In vitro*, fingolimod was shown to activate S1P receptors on astrocytes, stimulating intracellular pathways that regulate a variety of functions such as cell proliferation and migration.(3) Other studies, also in cell culture, demonstrated that fingolimod improved the survival and increased the number of progenitor and mature oligodendrocytes. (4,5) Furthermore, fingolimod, when directly administered in the brain of rats, in doses which did not induce any effect in circulating lymphocytes, significantly suppressed the severity of

clinical Experimental Autoimmune Encephalomyelitis (EAE). This clinical improvement was associated with enhanced myelization and axonal protection (6)

The clinical experience with fingolimod is already extensive. In clinical trials, to date over 15000 MS patients have been exposed to single or multiple doses of fingolimod. Based on this experience, pharmacodynamic effects ascribed to fingolimod are: 1) a rapid and persistent reduction of the peripheral lymphocyte count that is reversible after treatment discontinuation, 2) a predictable reduction in heart rate that is maximal upon treatment initiation and attenuates over time under continued treatment, 3) a mild- to moderate increase in airway resistance early after treatment initiation. The molecular basis of these effects is well understood and compatible with the known mode of action of fingolimod via engagement of S1P receptors.

An increased incidence of macular edema has been observed with fingolimod (in combination with cyclosporine A) in the renal transplantation studies. Regular ophthalmic monitoring in the ongoing clinical development program in RRMS patients has revealed cases of macular edema both prior to and after study drug initiation. The risk of macular edema in multiple sclerosis studies is currently under evaluation in the ongoing program, in which all patients are undergoing regular ophthalmology evaluations.

Multiple sclerosis (MS) is a neurodegenerative disease in which both demyelination and axonal loss occur.

Cognitive impairment is a major problem in MS and adversely affects patients' quality of life. Cognitive decline may appear early in the disease process and has been reported even at disease onset. It has previously been shown that a cognitive impairment is present in 53.7% of RRMS patients evaluated at the early disease stage during the onset of neurological symptomatology. (7,8)

Neuronal loss has been historically detected through MRI quantification of brain volume. Gray matter atrophy occurs in patients with relapsing forms of MS early in the disease course, has a major relationship to physical disability and cognitive impairment, and is a putative measure of neuroprotective therapeutic effects. (9)

The paired thalamic nuclei are gray matter structures on both sides of the third ventricle and are involved in a wide range of neurological functions including motor, sensory, integrative, and higher cortical functions.(10) Thalamic location, unique neurologic functions, widespread cortical and subcortical connections and vulnerability to MS pathology from the earliest clinical disease stages make it a critical structure for examining neurodegeneration in MS (11,12)

Cognitive dysfunctions are mainly associated with brain atrophy especially cortical grey matter. (13,14) In this study we will investigate the correlations between the effects of fingolimod on cognitive performances and MRI data.

For diagnostic, prognostic and treatment monitoring purposes, biomarkers which reflect the various neurodegenerative processes, would be helpful. The biomarker has to be central nervous system (CNS) specific, and available in concentrations that could be measured in cerebrospinal fluid (CSF) or blood. Serum and CSF oxysterols and cholesterol precursors have been linked to pathological processes in MS in previous studies, and seem to be promising candidate biomarkers. (15-17)

